#### 6.9.9 Treatment-Emergent Adverse Events

All AEs that occur after the first administration of the study drug will be regarded as treatment emergent. All AEs occurring from signing informed consent up to the first administration of the study drug will also be collected and will be referred to as non TEAEs.

A potential risk associated with the administration of Coagulation Factor VIIa (Recombinant) is the occurrence of an allergic type reaction to either the recombinant molecule or any of the potentially present host related impurities. Specific emphasis will be put on the observation of the patient after administration of the study drug to detect the occurrence of any potential allergic reaction. Symptoms of such reaction may consist of, but are not limited to:

- Skin redness, rash, hives
- Mucosal and/or skin swelling
- Difficulty breathing
- Hypotension
- Headache
- Dizziness
- Nausea

If any one or more of these symptoms occur, the responsible physician at the site should assess the patient and determine whether the symptoms are consistent with an acute allergic reaction and treat the symptoms accordingly.

Although reported to be rare in hemophilia patients, a potential risk associated with the administration of LR769, Coagulation Factor VIIa (Recombinant) is an exaggerated PD action, leading to a thromboembolic event. Specific emphasis will be put on the observation of the patient directly after administration of the study drug as well as during the follow-up visits to detect the occurrence of any thromboembolic events. Events that may occur are myocardial infarction, ischemic cerebrovascular accident, arterial thrombosis (e.g., aorta, intestinal), deep venous thrombosis (DVT), and pulmonary embolism (PE). In case signs and symptoms of any of these occur in the patients during the study, the responsible physician at the site will need to assess the symptoms and order and review diagnostic procedures (ECG, ultrasound, CT, MRI, Doppler, D-dimer, etc.) as appropriate to confirm or refute the diagnosis. In case of symptoms suggestive of a DVT or PE, the guidelines for diagnosis as published by the American College of Physicians (Qaseem et al., 2007) is suggested as guidance for determining the need for additional diagnostic tools.

In case an acute allergic reaction or a confirmed thrombotic event occurs in association with the administration of the study drug, such event should be reported in the same manner and timelines as a Serious Adverse Event (see Section 6.9.8.2), even when it does not meet the criteria for seriousness as listed in Section 6.9.8.1.

## 6.10 Concomitant Medication Assessments

All concomitant medication that was used by the patient during participation in the study will be recorded in the patients' files and/or patients' diaries and subsequently recorded in the eCRF. Specific emphasis will be put on the recording of concomitant medication for the treatment of bleeding episodes as well as for the treatment of pain. Patients who receive factor VIII or factor IX concentrates as part of either treatment of a bleeding episode or ITI therapy will maintain a detailed record of the actual treatment dates, times and doses.

## 6.11 Study Stopping Rules

The study will be stopped (i.e., cease enrollment as well as treatment of already enrolled patients) in the following cases:

- The Data Monitoring Committee (DMC) recommends after their scheduled review, or after an ad-hoc meeting in case of an SAE, that the study should be (temporarily) stopped
- A confirmed thrombotic event has been reported in any of the patients treated in the study
- An acute allergic reaction, or signs and symptoms strongly indicative of such reaction, has occurred in association with the administration of LR769
- A patient develops a neutralizing antibody to LR769

If one of these events occurs, participating sites, competent authorities as well as all involved ECs/IRBs will be informed of the (temporary) stop of the study. Investigations into the case(s) will need to be done and the results will then be reported to the competent authorities and ECs/IRBs, together with a recommendation on whether and how to proceed with the

study. Only after approval of the competent authorities and ECs/IRBs may the study continue.

## **6.12 Removal of Patients from the Trial or Study Drug**

The investigator may withdraw a patient from the study for any of the following reasons:

- The investigator believes it is in the best interest of the patient to discontinue the study, or
- A protocol deviation occurs that makes the interpretation of the data not feasible, or
- A clinically significant change in a laboratory parameter occurs that does not allow safe administration of the study drug and/or interferes with the interpretation of the study results, or
- Lack of compliance with study requirements, or
- The sponsor or investigator terminates the study, or
- The patient requests to be discontinued from the study.

In case of early withdrawal of the patient, he will be asked to perform the end of study visit assessments, unless he has withdrawn informed consent.

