## **2 STUDY OBJECTIVES**

### **2.1 Primary Objectives**

The primary objectives of this study are:

- To assess the efficacy of 2 separate dose regimens (75 µg/kg and 225 µg/kg) of LR769 for the treatment of bleeding episodes in hemophilia A or B pediatric patients, from birth to <12 years old, with inhibitors to factor VIII or IX
- To assess the safety of LR769. This includes the immunogenic potential of the drug product

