### 3.1.3 Follow-Up Visits

Patients will be followed initially at 3 weeks ( $\pm 2$  days) and 6 weeks ( $\pm 5$  days) following the first administration in Phase A and subsequently every 6 weeks ( $\pm 5$  days). Patients may be treated for multiple bleeding episodes during the course of the study. All patients will be followed for at least 6 months after the first LR769 administration or, if the study ends, for 14 ( $\pm 2$  days) after the last administration of study drug.

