### 6.9.2 Timing

Adverse events will be collected from the time of signing of the informed consent until completion of the study. At each study visit the patient/parent will be asked to report any and all changes in health status or condition (AEs) experienced since the previous visit.

Additionally, the patient/parent will be asked specifically whether the patient experienced any signs and symptoms that may indicate a thromboembolic event occurred. These may include, among others, headache, shortness of breath, chest pain, cyanosis, calf pain, swelling/edema, redness, venous distension or pain on dorsiflexion of the foot.

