### **7.3.7 End of Study Visit/Early Termination Procedures**

- Immunogenicity sample
- Safety labs (hematology, chemistry)
- FVIII or FIX inhibitor sample for central lab
- Vital signs
- Physical examination, including check for physical signs of thromboembolic events
- AE assessment

- Healthcare utilization assessments
- Assessment of concomitant medication
- Drug accountability and patient diary collection

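### Section 6.12 gives no way to stop LR769 and stay in follow-up, so a child withdrawn because dosing is unsafe has one termination visit in place of serial safety sampling to 6 months

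*Protocol*

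**What the plan says.** Protocol section 6.12 is titled "Removal of Patients from the Trial or Study Drug", which names two different events. The text then provides for one: "The investigator may withdraw a patient from the study for any of the following reasons". The reasons listed include "A clinically significant change in a laboratory parameter occurs that does not allow safe administration of the study drug", as well as protocol deviation and poor compliance. After early withdrawal the child has one further contact: "he will be asked to perform the end of study visit assessments, unless he has withdrawn informed consent".

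That visit is set out in section 7.3.7, "End of Study Visit/Early Termination Procedures". It includes an immunogenicity sample, hematology and chemistry, an inhibitor sample, vital signs, a physical examination with a thromboembolic check, and adverse event assessment.

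Section 3.1.3 sets the planned minimum: "All patients will be followed for at least 6 months after the first LR769 administration". The exception stated there is the end of the study, when follow-up is 14 days after the last dose. Section 2.1 makes safety a primary objective and adds: "This includes the immunogenic potential of the drug product".

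**The concern.** A laboratory change that makes dosing unsafe is a reason to stop giving LR769. It is not in itself a reason to stop observing the child. Section 6.12 nevertheless handles it by withdrawal from the study, and no other section defines a status of being off drug but still on study. The passages on rescue (3.1.2.4, 7.2.3) and surgery (3.1.2.5) interrupt LR769 for a time and expect the child to return to it. Section 6.11 covers neutralizing antibody, acute allergic reaction and confirmed thrombosis by stopping the study for everyone. It does not say how the affected child is followed.

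The antibody schedule is serial, and a positive result that develops late is seen only if later samples are taken. If children who stop for a safety reason differ in their later safety outcomes, the missing samples and adverse events may be informative. In a trial of about 24 children, each unobserved event carries weight.

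**Working it through.** **The passages together.** Heading of 6.12: trial or drug. Action in 6.12: study only. Minimum follow-up in 3.1.3: 6 months for all. Data after withdrawal: one visit (6.12, 7.3.7). For adverse events, section 6.9.2 says "Adverse events will be collected from the time of signing of the informed consent until completion of the study". Section 6.9.1 follows events to resolution or 30 days after the termination visit, whichever is first. Section 6.9.8.2 requires reporting of SAEs within 30 days of the last dose.

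**The plan's own figure.** Section 9.2 claims power of at least 80% with 22 patients, 8 episodes per regimen each, success rates of 0.70 against 0.55, correlation 0.1 and one-sided alpha 0.0125.
- Episodes: 22 × 8 × 2 = 352, as stated.
- Design effect: 1 + (8 − 1) × 0.1 = 1.7. Effective n per regimen: 176 / 1.7 = 103.5.
- Standard errors: √(0.55 × 0.45 / 103.5) = 0.0489 under the null and √(0.70 × 0.30 / 103.5) = 0.0450 under the alternative. The critical z is 2.241.
- Power: Φ((0.15 − 2.241 × 0.0489) / 0.0450) = 81.5% with the null standard error in the critical value, or Φ(0.15 / 0.0450 − 2.241) = 86.2% with the alternative one throughout.

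The claim reproduces. With 21 patients the two versions give 79.4% and 84.4%, and section 6.13 allows replacement. Efficacy power is not what is at risk here.

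**Samples and observation lost.** Appendix 1 schedules post-dose antibody samples at weeks 3, 6, 12, 18 and 24. I assume that withdrawal comes just after the visit shown, that the termination visit follows promptly, and that week 24 stands for 6 months.
- Net samples lost = scheduled samples remaining − 1 termination sample.
- Weeks outside the window = 24 − week of withdrawal − 30/7.

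| Withdrawn | Samples remaining | Net lost of 5 | Weeks to week 24 | Weeks beyond 30 days |
|---|---|---|---|---|
| Before week 3 | 5 | 4 | 24 | 19.7 |
| After week 3 | 4 | 3 | 21 | 16.7 |
| After week 6 | 3 | 2 | 18 | 13.7 |
| After week 12 | 2 | 1 | 12 | 7.7 |
| After week 18 | 1 | 0 | 6 | 1.7 |

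The 30-day cover is itself partial. It applies to adverse events already under follow-up and to SAEs close to the last dose.

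**Illustration.** Suppose, purely as an assumption, that two children would have become antibody-positive after withdrawal and are not seen. Section 9.3 defines the Safety Population as all treated patients, so both stay in the denominator.
- Reported: 0/24. One-sided 95% upper limit: 1 − 0.05^(1/24) = 11.7%.
- Had they been followed: 2/24 = 8.3%. The exact upper limit solves P(X ≤ 2 | n = 24, p) = 0.05. At p = 0.240 the three terms are 0.0014 + 0.0105 + 0.0380 = 0.0498, so the limit is 24.0%.

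**The case against.** The strongest reply is that this is ordinary protocol structure: a general follow-up rule and a clause for early withdrawal. Several parts of that reply stand.

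- A reader might infer that 6.12 flatly contradicts 3.1.3. The documents do not go that far. Section 3.3 and the synopsis qualify each child's length of participation for premature discontinuation. The two sections are unreconciled, not irreconcilable.
- A reader might infer that a child who cannot be dosed must leave. Section 6.12 is permissive. Treatment in Phase B is given only when a bleed occurs, and visits are timed from the Phase A dose (7.3), so attending without being dosed is already workable. Even so, 6.12 names no alternative status, and sites may apply it differently.
- A reader might infer that safety and antibody data are lost altogether, or that withdrawal after week 6 costs 3 of the 5 samples. The termination visit includes an antibody sample, safety labs and an examination, so the net loss after week 6 is 2.
- A reader might infer that withdrawn children drop out of the safety denominator. Section 9.3 keeps them in.
- A reader might infer that the loss falls on the children who matter most for immunogenicity. The gravest events come under 6.11, and nothing in the documents says that children with the laboratory changes in 6.12 are likelier to develop antibodies. That the loss is informative is possible but not shown.

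The reply does not supply a route for stopping LR769 while staying in follow-up, and 6.11 does not fill that gap.

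**Conclusion.** The point holds as a gap in the plan for data collection after LR769 is stopped. Section 6.12 announces removal from study drug and provides only for withdrawal from the study. A child withdrawn under it has one termination visit and 30-day windows in place of the follow-up in 3.1.3. The net cost is 0 to 4 of 5 antibody samples by week 24 and about 2 to 20 weeks of observation, and it is largest for early withdrawals.

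The sizes rest on a prompt termination visit and on week 24 as 6 months. The contrast of 0/24 with 2/24 rests on an assumed two missed positives. It shows how sensitive a trial of this size is and does not predict what will happen. The two children enrolled beyond the 22 needed are a margin for dropouts and unevaluable bleeds (9.2), not a forecast of safety withdrawals.

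The main SAP (version 2.0) is not among the documents. Its addendum does not address withdrawals. The change is worth making because it is cheap and serves a primary objective.

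**What to change.** In section 6.12, with cross-references in 6.11 and 3.1.3, distinguish stopping LR769 from withdrawing from the study. State that a child who stops LR769 is asked to keep the visits already scheduled to at least 6 months after the first dose. These carry the adverse event and thromboembolic checks, the immunogenicity samples, and safety labs where listed. Two exceptions apply: the parents have withdrawn consent, or the investigator judges that leaving the study is in the child's best interest. No rule is proposed on when LR769 should be stopped.

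No new assessment is added, and section 9.3 already keeps treated bleeds in the efficacy analysis. The cost is protocol wording plus the remaining scheduled visits and their blood draws for the few children concerned. By Table 2 these draws range from 2.5 to 14 mL per visit between week 3 and week 24, depending on weight and visit. The existing arrangements for children under 12 kg would continue to apply.

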## **6.13 Replacement of Patients**

Patients who are withdrawn will only be replaced if the minimum number of patients/bleeding episodes needed for Phase A or Phase B will not be met.

## **6.14 Other Study Procedures**

For the healthcare resource utilization assessments, the direct healthcare costs will be determined by collecting data on use of product, number of visits to hospital/hemophilia treatment center, days of inpatient hospitalization and use of concomitant treatments. Secondary economic effects will be assessed by collecting data on days away from school or work.

## **6.15 Appropriateness of Measurements**

Efficacy assessments are done according to existing guidelines and published literature. The patient/parent is the best person to assess the effect of the treatment on the bleed, as it most often is an internal bleeding episode in a joint or soft tissue.

Occurrence of pain and progression/resolution of pain is assessed at each efficacy assessment timepoint. Pain caused by a bleeding episode will be measured in the patient diary on a VAS in millimeters from 0 (no pain) to 100 (worst possible pain).

Analysis of concomitant medications will be performed in the trial with a focus on clotting factors (FVIII, FIX, FVIIa), blood products, analgesics, anti-inflammatory agents, and other drugs that may impair platelet and/or coagulation function.

## 7 STUDY ACTIVITIES

### 7.1 Phase A: Initial Safety and PK Phase

#### 7.1.1 Screening (Days -21 to -1)

- Informed consent signature
- Determine eligibility
- Demographics (Date of birth, race/ethnicity, sex)
- Medical history
- Physical examination, including height and weight
- Safety labs (hematology, coagulation, chemistry), by central lab
- Vital signs
- Assessment of concomitant medication
- Assessment of AEs

#### 7.1.2 Visit 1 (Day 0) Procedures

At randomization, patients will also be assigned to a specific PK sampling schedule. Half of the patients will be assigned to sampling schedule 1: at 10±2 minutes, 1 and 4 hours ( $\pm 10$  minutes). The other half will be assigned to sampling schedule 2: at 30±5 minutes and 2 and 8 hours ( $\pm 10$  minutes) relative to the start of infusion of study drug.

##### 7.1.2.1 Predose

- Confirmation of eligibility (patient should not have received any FVIIa product within 24 hours prior to study drug administration)
- Physical examination
- Vital signs
- Randomization
- Blood sample for Pharmacokinetic Assessment
- Assessment of concomitant medication
- Assessment of AEs
- Immunogenicity sample

##### 7.1.2.2 Drug Administration (0 min)

- A  $\leq 2$  minute IV push of 75  $\mu\text{g}/\text{kg}$  or 225  $\mu\text{g}/\text{kg}$  of LR769, depending on dosing randomization of the patient
- Assessment of AEs

7.1.2.3 10±2 min after start of infusion

- Blood sample for PK Assessment (when assigned to sampling schedule 1)
- Assessment of AEs

7.1.2.4 30±5 min after start of infusion

- Vital signs
- Blood sample for PK Assessment (when assigned sampling schedule 2)
- Assessment of AEs

7.1.2.5 1 hour ±10 minutes after start of infusion

- Vital signs
- Blood sample for PK Assessment (when assigned to sampling schedule 1)
- Assessment of AEs

7.1.2.6 2 hours ±10 minutes after start of infusion

- Vital signs
- Blood sample for PK Assessment (when assigned to sampling schedule 2)
- Assessment of AEs

7.1.2.7 4 hours ±10 minutes after start of infusion

- Vital signs
- Blood sample for PK Assessment (when assigned to sampling schedule 1)
- Assessment of AEs

7.1.2.8 8 hours ±10 minutes after start of infusion

- Vital signs
- Blood sample for PK Assessment (when assigned to sampling schedule 2)
- Assessment of AEs

## 7.2 Phase B: Treatment of a Bleeding Episode

Treatment of any bleeding episode will be initiated as soon as possible, but certainly within 4 hours of first symptoms of the onset of the bleeding episode.

## 7.2.1 Mild/Moderate Bleeding Episode Procedures

### 7.2.1.1 Pre treatment

- AE assessment
- Assessment of concomitant medication
- Bleeding Episode Characteristics
  - Location
  - Date/Time of start of bleeding episode
  - Severity
  - Spontaneous/traumatic
- Patient Diary

### 7.2.1.2 Treatment (Time 0 hrs)

- A  $\leq$  2 min IV push of 75 or 225  $\mu$ g/kg of LR769, depending on the dosing randomization of the patient and the 12 weeks treatment regimen he is in at the time of bleeding episode
- Record date, time and total dose of study drug as well as number and lot of vials used for preparation in patient diary (patient/parent); if in hospital or hemophilia treatment center in patient records by study staff
- AE assessment
- Assessment of concomitant medication

### 7.2.1.3 3, 6, 9, 12, 15, 18, 21 hours after first administration

- AE assessment (assessed over a period of 21 hours after first study drug administration, reported by the patient/parent in the patient diary if home treatment and in addition by study staff if in hospital or hemophilia treatment center)
- Efficacy assessments (within 15 minutes before each new administration of the study drug) to be done by the patient/parent if home treatment and by study staff if in hospital or hemophilia treatment center in addition to patient assessments
- Record date, time and outcome of the assessments in patient diary (patient/parent); if in hospital or hemophilia treatment center in patient records by study staff in addition to patient's assessment
- Assessment of concomitant medication

### **ADMINISTRATION OF STUDY DRUG:**

#### When in 75 $\mu$ g/kg dose treatment regimen:

- If response to treatment 3 hours after last administration is unsatisfactory (i.e., efficacy assessment is not rated as good or excellent): a  $\leq$  2 min IV push of 75

$\mu\text{g}/\text{kg}$  of LR769 may be administered. This may be repeated, if needed every 3 hours up to and including 21 hours after first administration.

- If response to treatment 3 hours after the first or any of the subsequent administrations is satisfactory (i.e., efficacy assessment is rated as good or excellent): no study drug administration. Perform the 3 hourly efficacy assessments until 3 hours after the last administration as well as the 12 hours efficacy assessments (if not already done).

#### When in 225 $\mu\text{g}/\text{kg}$ dose treatment regimen:

- If response to treatment 9 hours after first administration is unsatisfactory (i.e., efficacy assessment is not rated as good or excellent): a  $\leq 2$  min IV push of 75  $\mu\text{g}/\text{kg}$  of LR769 may be administered. This may be repeated, if needed every 3 hours up to and including 21 hours after first administration.
- If response to treatment 9 hours after first administration, or 3 hours after any subsequent administrations, is satisfactory (i.e., efficacy assessment is rated as good or excellent): no study drug administration. Perform the 12 hours efficacy assessments (if not already done).
- Record date, time and total dose of study drug as well as number and lot of vials used for preparation in patient diary (by the patient/parent); if in hospital or hemophilia treatment center in patient records by study staff.
- If, because of an initial sufficient response at 9 hours post initial dose of study drug, no additional study drug is administered, it may re-started before the 24-hour cut off in case of a recurrence of a bleeding episode. This should be noted in the patient's diary.

### **24 HOURS AFTER FIRST ADMINISTRATION**

- AE assessment
- Efficacy assessments. If the response to treatment is still unsatisfactory (i.e., efficacy assessment is not rated as good or excellent): do not administer any more study drug. Alternative treatment should be initiated in consultation with the study staff.
- Record date, time and outcome of the assessments in patient diary (by the patient/parent); if in hospital or hemophilia treatment center in patient records by study staff in addition to patient's assessment
- Assessment of concomitant medication

#### **7.2.2 Severe Bleeding Episode Procedures**

Severe bleeding episodes always need to be treated in a hospital or hemophilia treatment center. Exception may be the first administration for the treatment of a bleeding episode, which can be done at home if the patient qualifies for that (see Section 3.1.2.3).

